Acute Day Units as Crisis Alternatives to Residential Care AD-CARE

Chief Investigator:

[name], UCL

Supported by:

NIHR HS&DR 15/24/17

Sponsored by:

[figure not shown]
University College London (UCL)

Protocol version number and date:

2 20/12/16

R&D / Sponsor Reference Number(s): 16/0576

Study Registration Number:

PROTOCOL VERSIONS

Version Stage	Versions No	Version Date	Protocol updated & finalised by;	Appendix No detail the reason(s) for the protocol update
Previous	1	25/10/16	[name]	N/A
Current	2	20/12/16	[name]	1

DECLARATIONS

The undersigned confirm that the following protocol has been agreed and accepted and that the investigator agrees to conduct the study in compliance with the approved protocol and will adhere to the Research Governance Framework 2005 (as amended thereafter), the Trust Data & Information policy, Sponsor and other relevant SOPs and applicable Trust policies and legal frameworks.

I (investigator) agree to ensure that the confidential information contained in this document will not be used for any other purposes other than the evaluation or conduct of the clinical investigation without the prior written consent of the Sponsor.

I (investigator) also confirm that an honest accurate and transparent account of the study will be given; and that any deviations from the study as planned in this protocol will be explained and reported accordingly.

Chief Investigator:		
Signature:		Date/
Print Name(in full):		
Position:		
On behalf of the Study Sponsor:		
Gaislans.		
Signature:		Date 15/11/2016
Print Name(in full): [name]		
Position: Research Portfolio Coordin	nator	

STUDY SUMMARY

Identifiers	
IRAS Number	201627
REC Reference No	
Sponsor Reference No	16/0576
Other research reference	
number(s) (if applicable)	
Full (Scientific) title	Acute Day Units as Crisis Alternatives to Residential Care
Health condition(s) or	
problem(s) studied	
Study Type i.e. Cohort etc	Observational cohort study, and qualitative study
Target sample size	Cohort study: n=800, qualitative study: n=55
STUDY TIMELINES	
Study Duration/length	Three years
Expected Start Date	01/07/16
End of Study definition	30/06/19
and anticipated date	
Key Study milestones	IRAS form submitted, REC attended, first participant recruited, final
	participant recruited
FUNDING & Other	
Funding	NIHR HS&DR
Other support	
STORAGE of SAMPLES	
(if applicable)	
Human tissue samples	N/A
Data collected / Storage	N/A

There are well-established and publicised problems in acute mental health care for people experiencing crises. This includes poor experience, lack of provision of recommended interventions, delays in accessing care, poor continuity of care, over-reliance on restriction and the current reduced bed capacity. There are a range of reports regarding the need for better crisis care including the Schizophrenia Commission report¹ in 2012, the Chief Medical Officer's report in 2013² and the 2015 interim Crisp report for the Commission on Acute Adult Psychiatric Care³.

We need to provide better, more efficient, acceptable, empowering community responses to acute mental health crises. Inpatient psychiatric care is unpopular, expensive and sometimes detrimental for individuals and their families. There are also criticisms of crisis resolution/home treatment teams (CRTs) in terms of the limited interventions they provide, the time-limited assessment/treatments they can offer, and the lack of consistency in staff due to the need to provide 24 hour care via a shift system.

Acute Day Units (ADUs) are services which have the potential to address these needs and overcome problems in both inpatient and crisis/home treatment settings. ADUs are available to enhance mental health crisis care in some English catchment areas (about 1 in 5 English crisis teams have access to ADUs). These units offer intensive, short term community responses to mental health crises, and aim to reduce costly and unpopular admissions, either avoiding them or facilitating early discharge.

ADUs (called day hospitals in the past) have been a component of adult mental health services for decades, especially across Europe⁴ but their provision and function in the UK has been highly variable, and research is relatively lacking⁵. They also did not form a core part of the NHS Service Framework. A survey conducted in 2001 (pre-crisis teams) identified 102 such services in England providing a mixture of care models, including i) an alternative to

admission, ii) more chronic care and iii) services for those for whom outpatient care was insufficiently intensive Cochrane systematic reviews have compared acute day hospitals to both outpatient and inpatient care^{7,8}. We will only focus on acute units which crisis teams have access to for supporting urgent mental health crises. We found 41 such units in The NIHR CORE programme grant survey in 2013. The limited available evidence is heterogeneous in terms of study participants, design and outcomes, making conclusions difficult. A meta-analysis of four randomised controlled trials concluded that mental health day units were superior in terms of clinical outcomes (symptoms) and were less costly⁴. However the most recent British RCT, involving one London acute day unit in 2006, reported that while symptom improvement and satisfaction were greater, the costs were also greater⁹.

Service users and crisis team staff tell us that ADUs can be very valuable but they need to be safe and to include effective psychological and pharmacological interventions, peer support (as recommended by NICE¹⁰) and a smooth care pathway including interface with external user-empowering agencies in the community. The integration of the acute system seems key, as well as its ability to target the right people at the right time and to be value for money. Local evaluations suggest ADUs have high levels of satisfaction and they fit with many aspects of the NHS plan such as patient empowerment and innovative models of acute care¹¹.

There is a dearth of information regarding modern ADUs such as their models of care, effectiveness, place in the acute pathway and service user acceptability and experience. The research we propose addresses problems identified by a range of recent publications and policies regarding acute mental health care. The Crisis Care Concordat¹² includes crisis care and acute day care within its domains. ADUs address many of the ambitions of the NHS 5 year plan¹³, including improvements in acute care, personalised care, empowerment and efficiency.

2 Workpackage 2.1 – Cohort Study

OBJECTIVES

In this stage of the AD-CARE study, we aim to:

- 1. Describe the clinical and socio-demographic characteristics of people who use each of five ADUs selected for the in depth case studies
- 2. Determine their pathways into the ADU, length of stay, treatments received, experience, empowerment, loneliness and readmissions at 6 months
- 3. Compare these characteristics to a cohort of people who receive acute crisis care without ADU input

STUDY DESIGN

This will be a cohort study. Five ADUs will be identified from the national survey carried out in WP1. We will invite people aged 18 and over who are consecutively admitted to each ADU to participate in baseline interviews and then telephone/internet follow-up 8-12 weeks after baseline, with administrative outcome data collected at 6 months.

We will invite people form the same crisis pathway to participate in the parallel non-ADU cohort. They must be receiving CRT home treatment when recruited, but could previously have been admitted to an inpatient ward during this episode.

We aim to recruit 80 people who receive ADU care and 80 people who do not, in the locality of each ADU chosen for the mixed-method case studies. This gives a total of 400 in each 'arm', and a combined total of 800.

STUDY SCHEDULE 5

At baseline, ADU staff will screen all service users consecutively admitted to their service from the start date. All service users who meet the inclusion criteria will be approached by ADU staff and asked if they are willing to be contacted by researchers to discuss participation further (except at sites where service users have already given consent to be contacted directly about research projects: in this circumstance, researchers will contact service users directly once their eligibility and any risk-related safety requirements have been established). The researchers will keep a record of potential participants to be contacted and the date and the name of the clinician with whom this was agreed. Researchers will ask the clinician who spoke to each service user to note the patient's agreement to be contacted by a researcher in their patient records. Those who agree will be contacted by a researcher with an information sheet and offer to answer any questions. Potential participants will be given at least 24 hours to consider whether they would like to take part, and then if still interested they will be consented by a researcher, who will also collect the baseline data.

Participants will be contacted by phone 8-12 weeks after baseline to be asked if they are willing to complete the questionnaire again. If so, the researcher will collect the data required from them. If a participant does not wish continue at follow up they are free to decline.

If any participant wishes to withdraw at any point they are free to do so without any detriment to their current or future care. Unless participants inform researchers that they do not want their data used, any data collected before withdrawal will be used.

The study will be completed by 30/06/2019, with the recruitment of 800 participants.

CONSENT

As noted above, data will be collected by study researchers and Clinical Research Network (CRN) staff (hereafter collectively referred to as 'researchers'). At baseline, ADU staff will screen all service users consecutively admitted to their service from the start date. All service users who meet the inclusion criteria will be approached by ADU staff and asked if they are willing to be contacted by researchers to discuss participation further (except at sites where service users have already given consent to be contacted directly about research projects: in this circumstance, researchers will contact service users directly once their eligibility and any risk-related safety requirements have been established). The researchers will keep a record of potential participants to be contacted and the date and the name of the clinician with whom this was agreed. Researchers will ask the clinician who spoke to each service user to note the patient's agreement to be contacted by a researcher in their patient records. Those who agree will be contacted by a researcher with an information sheet and offer to answer any questions. Potential participants will be given at least 24 hours to consider whether they would like to take part, and then if still interested they will be consented by a researcher, who will also collect the baseline data.

In order to include those whose first language is not English, any local provision by NHS Trusts for translators will be used. However, where there are no translators provided locally it will not be possible to include non-English-speaking participants.

ELIGIBILITY CRITERIA 7

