7.1 Inclusion Criteria

Inclusion criteria are as follows:

- 18 years old or older
- Have used the ADU for at least one week
- Can read and understand English (or there are translation services in place to enable communication)
- Have capacity to provide informed consent
- Do not pose too high a risk to others or themselves to participate

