7.2 Exclusion Criteria

We will exclude patients who are too unwell to consent, but otherwise aim to be inclusive to gain a fully representative sample, including using local interpretation facilities when necessary.

RECRUITMENT

As noted above, researchers will recruit participants. At baseline, ADU staff will screen all service users consecutively admitted to their service from the start date. All service users who meet the inclusion criteria will be approached by ADU staff and asked if they are willing to be contacted by researchers to discuss participation further (except at sites where service users have already given consent to be contacted directly about research projects: in this circumstance, researchers will contact service users directly once their eligibility and any risk-related safety requirements have been established). The researchers will keep a record of potential participants to be contacted and the date and the name of the clinician with whom this was agreed. Researchers will ask the clinician who spoke to each service user to note the patient's agreement to be contacted by a researcher in their patient records. Those who agree will be contacted by a researcher with an information sheet and offer to answer any questions. Potential participants will be given at least 24 hours to consider whether they would like to take part, and then if still interested they will be consented by a researcher, who will also collect the baseline data. Participants will be offered £20 in cash as a thank you for taking part (£10 for the baseline interview, and £10 for the follow up interview at 8-12 weeks after baseline). If participants decline this money it will be returned to the study. Participants will be contacted by phone by a researcher 8-12 weeks after baseline in order to collect follow up data. At 6 months after baseline, participant data will be collected from patient records and clinical notes.

While many people find talking about their experiences to be helpful, some people may find that completing the questionnaire brings up issues that cause emotional distress. In this case the researcher will provide immediate emotional support to the participant, offer to pause or postpone the interview, and, if the participant asks, will contact a person of the participant's choice (e.g. current care coordinator, carer, friend, family member, colleague) for them.

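### Objectives 1 and 2 describe the people who use each ADU, but the cohort contains only consenting users with at least one week's stay, so length of stay is truncated at 7 days

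*Protocol*

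**What the plan says.** Protocol section 3 (Workpackage 2.1) sets as objective 1: "Describe the clinical and socio-demographic characteristics of people who use each of five ADUs selected for the in depth case studies". Objective 2 refers to the same people: "Determine their pathways into the ADU, length of stay, treatments received, experience, empowerment, loneliness and readmissions at 6 months". Neither states a minimum stay. Section 4 says that people admitted consecutively to each ADU will be invited.

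Section 7.1 then limits entry. Among its criteria are "Have used the ADU for at least one week" and "Do not pose too high a risk to others or themselves to participate", together with capacity and either English or available translation. Section 7.2 adds: "We will exclude patients who are too unwell to consent, but otherwise aim to be inclusive to gain a fully representative sample". Sections 5, 6 and 8 also require agreement to be contacted (or prior research consent at some sites), at least 24 hours to consider, and consent. The six-month extraction from records in section 8 covers participants only.

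On record keeping, ADU staff screen all consecutive admissions. The one pre-consent record described is the researchers' list: "The researchers will keep a record of potential participants to be contacted and the date", with the clinician's name.

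**The concern.** The population named in the objectives is not the population sampled. For most of the listed items this is ordinary selection, whose effect has no known sign. Length of stay is different, because the entry rule is itself a rule about length of stay: every stay shorter than a week is missing from the distribution that objective 2 sets out to determine.

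This matters because section 1 justifies the study by how little is known about modern ADUs, including their place in the acute pathway. Who uses these units, and for how long, is central to that. People who leave in the first week may differ in how they arrived, what they received and where they went next, so their absence also affects the profile and pathway descriptions. An analysis plan cannot repair this later, since stays that were never recorded cannot be recovered. The protocol specifies no screening log, and no data on people who are ineligible, leave early or refuse contact. As written, it provides no means of checking the representative-sample aim.

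**Working it through.** **Plan's own figure.** The protocol gives no length-of-stay figure to reproduce. Its only calculation, 310 per arm inflated to 400 for readmission (section 9), is not an input here.

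**Inputs.** The floor c = 7 days comes from section 7.1. The stay distribution and its true mean m are not in the documents, so both are assumed and varied.

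**Direction.** With T the stay of any ADU user, the cohort estimates E[T | T ≥ 7] and the objective asks for E[T]. Since

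E[T] = P(T < 7)·E[T | T < 7] + P(T ≥ 7)·E[T | T ≥ 7],

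and the first conditional mean is below 7 while the second is at least 7, the floor raises the mean whenever P(T < 7) > 0. It changes nothing when P(T < 7) = 0.

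**Exponential stay, mean m.** Share lost = 1 − exp(−7/m); observed mean = m + 7.

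| m (days) | Share lost | Observed mean (days) | Overstatement |
|---|---|---|---|
| 20 | 1 − exp(−0.350) = 30% | 27 | 7/20 = 35% |
| 30 | 1 − exp(−0.233) = 21% | 37 | 7/30 = 23% |
| 45 | 1 − exp(−0.156) = 14% | 52 | 7/45 = 16% |

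**Gamma stay, shape 2, mean m.** Put x = 14/m. Share lost = 1 − (1 + x)·exp(−x); ratio of observed to true mean = (1 + x + x²/2)/(1 + x).

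| m (days) | x | Share lost | Ratio | Overstatement |
|---|---|---|---|---|
| 20 | 0.700 | 16% | 1.945/1.700 = 1.144 | 14% |
| 30 | 0.467 | 8% | 1.576/1.467 = 1.074 | 7% |
| 45 | 0.311 | 4% | 1.360/1.311 = 1.037 | 4% |

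**Mixture, stated by early-leaving share.** Suppose a share f leaves before day 7 with mean stay 3.5 days, and the rest have mean L. The overstatement is L/(3.5f + (1 − f)L) − 1. With L = 30 and f = 10% this is 30/27.35 − 1 = 9.7%. Over L = 21 to 42 it is 0% at f = 0, about 4–5% at f = 5%, 9–10% at f = 10% and 20–22% at f = 20%.

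**Range.** A lognormal stay with log-SD 0.5 to 0.8 and mean 14 to 42 days gives 0% to 32%. The largest figure computed is an exponential stay with mean 14 days: 7/14 = 50%. The assumed cases therefore span 0% to about 50%.

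**The case against.** The strongest reply is that this is a matter of wording and reporting. The eligibility rule is openly stated, the exclusion of people too unwell to consent is given in the same sentence as the representative-sample aim, and neither the primary outcome nor the sample size is touched. That is right as far as it goes. It does not remove the mismatch between objectives 1 and 2 and section 7.1, because following the plan as written answers a different question about length of stay.

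Four stronger readings are tempting, and the documents do not support them.

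- *The cut-off is 8 days, a week plus the 24-hour consideration period.* The criterion asks only that the person has used the ADU for a week, not that they are still attending at consent, and section 10 allows consent by telephone. The floor is 7 days.
- *No record is kept of anyone outside the cohort.* The protocol is silent on how screening is logged; it does not say that nothing is kept. People who agree to contact and then decline are on the researchers' list. What can be said is that no screening log and no data on non-participants are specified.
- *Length of stay is certainly overstated.* That holds only if some users leave within a week, which the documents neither show nor exclude. Consent, capacity and risk selection could act in either direction.
- *The length-of-stay comparison with the crisis team (CRT) cohort is biased upward.* Objective 3 compares these characteristics between cohorts, but section 9 names no length-of-stay contrast. The CRT cohort must be under current home treatment when recruited (section 4), which tends to under-sample short episodes too. The net sign is unknown.

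**Conclusion.** The point holds for the descriptive objectives. The stated target is all users of each ADU; the plan delivers consenting users with at least one week's stay. Relative to all users, the one-week floor can only raise mean length of stay or leave it unchanged. Its size cannot be known from the documents. Under the assumed distributions with true means of 20 to 45 days, the overstatement is 16% to 35% for exponential stays and 4% to 14% for gamma (shape 2) stays, and it is zero if nobody leaves in week one. These figures isolate the floor and leave out the other selection steps, whose effect cannot be signed. The change should be made, but the readmission analysis does not depend on it.

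**What to change.** Leave eligibility and sample size as they are, and do two things.

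1. Restate objectives 1 and 2 as applying to consenting people with at least one week of ADU use, and do not present the cohort's length of stay as that of all ADU users.
2. From the screening staff will already carry out, keep an anonymous tally of admissions with the reason each person was not approached or not enrolled. Ask each ADU for anonymised aggregate length of stay and basic characteristics for all admissions in the recruitment window, and report the cohort against that denominator.

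Treat any length-of-stay comparison with the CRT cohort as descriptive only, because the two cohorts are selected on duration in different ways.

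The first step is wording. The second costs one aggregate data request and one tally sheet at each of the five sites, with no extra participants or visits.

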If service users or carers report any untoward feedback, the researcher conducting the interview will confirm with the participant whether or not they would like the researcher to pass this on to the service or other relevant person. If the untoward feedback is of a nature that leads the researcher to be concerned for the safety of others, the participant will be informed that the feedback will be passed on to the relevant service or person to be addressed, but that if desired and possible they will remain anonymous.

STATISTICAL METHODS

We will provide descriptive statistics comparing the baseline characteristics of the CRT cohorts with and without ADU care within each of the five case studies and also for the

sample as a whole. We will explore baseline differences in demographics, diagnoses and symptom severity, severity of past mental health history and pathways into the crisis service using parametric and non-parametric tests as appropriate.

For the primary outcome we will compare the risk of readmission in the groups who do and do not receive ADU care using logistic regression adjusting for age, gender, main diagnostic group and a measure of severity.

We will compare satisfaction/ experience mean CSQ-8 scores in the two cohorts and use linear regression to adjust for important covariates. We will adjust for cluster (sampling unit being the ADU), and also test for effect modification by individual ADU. We will not make head to head comparisons of outcomes between ADUs.

For the economic evaluation we will also extract health service usage from clinical notes and apply unit costs from the sources described above, to estimate the costs incurred by participants during the 6-month follow-up period, and compare mean costs per patient with or without ADU care, controlling for confounders using baseline data.

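### The non-ADU cohort can include people the local ADU would not have taken, and nothing recorded at screening allows them to be identified

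*Protocol*

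**What the plan says.** Objective 3 (section 3) is to "Compare these characteristics to a cohort of people who receive acute crisis care without ADU input". Section 4 sets out the comparator: "We will invite people form the same crisis pathway to participate in the parallel non-ADU cohort". Its one comparator-specific condition follows: "They must be receiving CRT home treatment when recruited, but could previously have been admitted to an inpatient ward during this episode". Numbers are set by site: "We aim to recruit 80 people who receive ADU care and 80 people who do not, in the locality of each ADU".

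Section 7.1 gives a single inclusion list for the cohort study. Its service-related item is "Have used the ADU for at least one week". The item nearest to suitability is "Do not pose too high a risk to others or themselves to participate", which concerns taking part in the research and not acceptance by a day unit. Sections 5, 6 and 8 describe screening only for people admitted to the ADU, by ADU staff.

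The primary analysis in section 9 is to "compare the risk of readmission in the groups who do and do not receive ADU care" by logistic regression with four covariates: age, gender, diagnostic group and a severity measure. The sample size is built on an absolute reduction in readmission. CSQ-8 is compared by adjusted linear regression, and mean costs are compared with control for baseline confounders.

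**The concern.** Comparators come from localities where the crisis team already has access to an ADU. A CRT patient there who is not in the ADU may not have been offered it, may have declined it, may have found no place, or may have been judged unsuitable or been unable to attend. The first three kinds of patient have counterparts in the ADU cohort. The last does not.

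For people with no chance of ADU care, a regression has no ADU participants to compare them with and can only extrapolate. If their readmission risk differs for reasons outside the four covariates, the difference is attributed to ADU care. The same applies to CSQ-8 and costs. Nothing in the protocol records suitability or the reason for non-use, so the affected comparators could not be reliably identified afterwards.

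**Working it through.** **1. Can such people enter?** The conditions that apply to a comparator are the same pathway and locality, CRT home treatment at recruitment, no ADU care, age 18 or over, language, capacity, and acceptable risk for research participation. None refers to the ADU's acceptance or referral criteria. Taken literally, section 7.1 admits no comparator at all, because the ADU-use item cannot be met. Read without that item, it has no comparator equivalent. So such people can enter; how many would do so is not stated.

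**2. The plan's own figure.** Section 9 gives 310 per arm for 90% power at 50% v 36.8%, 45% v 32.0% or 40% v 27.4%, which are differences of 13.2, 13.0 and 12.6 points. With two-sided alpha 0.05 (assumed, as it is not stated), the two-proportion formula gives 295, 293 and 294 per arm. With continuity correction, n' = (n/4)[1 + √(1 + 4/(n·d))]², it gives 310, 308 and 310. Inflation gives 310 × 1.3 = 403, close to the stated 400. The sample size reproduces and is not in question.

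**3. Possible size of the bias.** Suppose ADU care has no effect. Let f be the share of comparators who are unsuitable, and e their readmission risk minus that of suitable people. Then:

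spurious difference = [(1 − f)·p + f·(p + e)] − p = f·e

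The protocol gives neither f nor e, so all values here are assumptions. With p = 35% and e = +15 points:

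| f | Comparator risk | Spurious difference |
|---|---|---|
| 20% | 0.8 × 35 + 0.2 × 50 = 38.0% | 3.0 points |
| 30% | 0.7 × 35 + 0.3 × 50 = 39.5% | 4.5 points |
| 50% | 0.5 × 35 + 0.5 × 50 = 42.5% | 7.5 points |

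With e = −15 points, the same shares give −3.0, −4.5 and −7.5 points, against ADUs. At f = 30%, a gap of 10 to 20 points gives 3 to 6 points.

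**4. Effect on the test.** Take p = 40% (the plan's lower baseline rate), a positive gap, and an effective 400/1.3 ≈ 308 per arm. The chance of a significant apparent benefit with no true effect (nominally 2.5% in that direction) is:

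| f | e | f·e | Share of 12.6 points | Chance |
|---|---|---|---|---|
| 10% | 10 | 1.0 | 8% | 4% |
| 20% | 20 | 4.0 | 32% | 17% |
| 30% | 20 | 6.0 | 48% | 32% |
| 40% | 30 | 12.0 | 95% | 85% |

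All these figures are before covariate adjustment, which would reduce them to the extent that unsuitability follows the four covariates. No figure is offered for CSQ-8 or costs.

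**The case against.** The strongest reply is that this is a declared observational cohort, that objective 3 defines the comparator by non-receipt of ADU care, and that the design recruits exactly that group. Pathway and locality are shared, only ADUs open to crisis teams are studied, severity is adjusted for, and section 9 plans baseline comparisons of severity, past history and routes into the crisis service. What remains would then be ordinary confounding by indication.

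Much of this stands, and it rules out several stronger readings:

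- A reader might infer that the cohort does contain people with no chance of ADU care. The protocol permits this but does not show it. It states no ADU acceptance criteria and no group an ADU refuses.
- The introduction might be read as making selection a defining function of ADUs: "as well as its ability to target the right people at the right time". There the word 'its' refers to the acute system, not to ADUs.
- A reader might take the primary question to be the effect among people who could have had ADU care. The protocol speaks of a reduction in readmission but never names that population.
- Adjustment might be called useless. If unsuitability works through diagnosis or severity, the model removes part of the gap, subject to its assumptions.
- The bias might be assumed to flatter ADUs. Section 1 says these units aim to avoid admissions or bring discharge forward, so they may take higher-risk people, which would reverse the sign.

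The reply does not remove the main point. Shared pathway and locality do not establish that the ADU would have accepted the person, and none of the planned baseline comparisons captures that. Although objective 3 is descriptive, the powered primary analysis is a contrast of outcomes. Nor can this be left to a statistical analysis plan, because a screening item that was never collected may not be recoverable.

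**Conclusion.** The point holds in a limited form. The protocol allows comparators for whom no ADU counterpart can exist, provides no usable criteria list for the non-ADU cohort, and records nothing that would separate these people out. The three outcome contrasts may therefore partly reflect ADU suitability, and the planned adjustment can address that only in part.

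Neither the size nor the sign of the bias can be determined from the protocol. The range of 3.0 to 7.5 points in either direction rests wholly on the assumed shares and the 15-point gap, and it is an unadjusted figure. It amounts to 3.0/12.6 = 24% up to 7.5/12.6 = 60% of the smallest planned effect, enough to matter for interpretation if the assumptions are near the truth. This is a worthwhile and inexpensive improvement. It does not show that the comparison is invalid.

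**What to change.** 1. In section 7.1, give the non-ADU cohort its own criteria list, without the ADU-use item and including the section 4 condition on CRT home treatment.
2. At screening, have the CRT clinician record for every comparator whether the person meets the local ADU's own referral criteria, and why the ADU was not used: not offered, declined, no place, or unsuitable or unable to attend.
3. In section 9, pre-specify that the readmission, CSQ-8 and cost comparisons are also reported with comparators limited to those marked suitable. Keep the full cohort for the descriptive objective.

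Excluding unsuitable people at entry would be the stricter alternative. It would rest enrolment on a clinician's hypothetical judgement that may vary by site, so recording the item is the more proportionate choice.

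The cost is one extra, partly subjective screening item and some precision in the restricted comparison. If 20% to 50% of 400 comparators were set aside, 320 to 200 would remain, and the standard error of the difference would grow by a factor of about √[(1/400 + 1/320)/(2/400)] = 1.06 to √[(1/400 + 1/200)/(2/400)] = 1.22, taking similar variances in both groups and a constant design effect. Confounding among suitable people, such as those who declined or were not offered a place, would remain.
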